Protocol Clinical Trial

Study synopsis

Study overview	
Title of clinical trial	Low grade inflammation in childhood obesity : an independent risk factor for endothelial dysfunction ?
Sponsor name	University Hospital of Brussels
Principal Investigator	prof. dr. [name] / [name]
Medical condition or disease under investigation	Obesity and overweight, cardiovascular risk factors
Purpose of clinical trial	To assess whether low grade inflammation in childhood obesity contributes to endothelial dysfunction
Primary objective	To investigate if the reactive hyperemia index by peripheral arterial tonometry is higher in adolescents with a history of childhood obesity and presenting a low grade inflammation in comparison with those without low grade inflammation (hSCRP < or > 1 mg/L)
Secondary objective (s)	To analyze the changes in hCRP and adiposity in obese children and adolescents after 5 to 10 years
Trial Design	Observational cohort study
Endpoints	RH-PAT scores, measured by peripheral artery tonometry . hSCRP, measured by automated immunoturbidometry BMI z-score and % body fat by skinfold thickness
Sample Size	54 (α= 0,05 – power 80%)
Summary of eligibility criteria	Overweight and obese adolescents, aged 12 to 21 years, with a known level of hs-CRP at initial evaluation for metabolic syndrome
Maximum duration of intervention	Single visit
Version and date of final protocol	Protocol version 1, date 18/08/2018
Version and date of protocol amendments	Not applicable

Study Schedule

Administrative information

1. Sponsor

The study is sponsored by the division of pediatric endocrinology of the University Hospital of Brussels (UZ Brussel).

2. (Principal) Investigator(s)

Prof. dr. [name]

Dr. [name]

[name]. [name]

[name] [name]

[name]

3. Departments involved

Department of Pediatrics

Division of Pediatric Endocrinology

University Hospital of Brussels

[name]

Ethical and regulatory information

1. Study registration

The study is registered at ClinicalTrials.gov and has a unique number: ####.

2. Study type

The study is an observational cohort study

3. Competent Ethics Committee

Central Ethics Committee:

Ethical Committee University Hospital of Brussels

[contact]

Email: [contact]

4. Ethical conduct of the study

The trial will be conducted in compliance with the principles of the Declaration of Helsinki (current version), the principles of Good Clinical Practice (GCP) and in accordance with all

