applicable regulatory requirements. This protocol and related documents will be submitted for review to Ethics Committee before start of the trial.

5. Declaration of conflict of interest

The investigators of this study declare that they don't have any competing interests.

6. Patient information and informed consent

The study will be conducted only after obtaining a prior informed consent of the legal representatives of the children and obtaining an assent of the children according to their age and maturity. The legal representatives of the children will sign an informed consent form and the assent of the children will be noted in the corresponding file. The informed consent form and the assent will be reviewed by the Ethics Committee prior to the start of recruitment.

7. Participant privacy and confidentiality

The investigators shall treat all information and data relating to the study disclosed to Participating Site and/or Investigator in this Study as confidential and shall not disclose such information to any third parties or use such information for any purpose other than the performance of the study. The collection, processing and disclosure of personal data, such as patient health and medical information is subject to compliance with applicable personal data protection and the processing of personal data (Directive 95/46/EC and Belgian law of December 8, 1992 on the Protection of the Privacy in relation to the Processing of Personal Data) as well as the General Data Protection of April 2018.

The data will be coded. There continues to be a link between the data and the individual who provided it. The research team is obligated to protect the data from disclosure outside the research according to the terms of the research protocol and the informed consent document. The subject's name or other identifiers are stored separately from their research data and replaced with a unique code to create a new identity for the subject.

8. Early termination of the study

Not applicable.

9. Protocol amendments

Changes to the study protocol will be submitted to the Ethics Committee and will not be performed before obtaining an approval.

10. Reward

Participant will not receive a compensation for their participation in the study. If needed, an absence certificate will be provided for the participant and/or the accompanying adult at the time of the study visit.

Background and rationale

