Obesity and overweight have become an important health burden in children and adolescents, with 19% of all children between 5 and 18 years being either obese or overweight in Belgium(1,2). Obesity and especially visceral adiposity early in life may contribute to the development of cardiovascular disease at older age, as it shows tracking into adulthood and is associated with cardiovascular risk

factors such as dyslipidemia, insulin resistance, arterial hypertension and low grade inflammation, in a variable percentage (4) (5)

Low grade inflammation, as assessed by hSCRP, was found to be present in 20.6 % and 19.8 % of overweight children and adolescents (6). In adults, hSCRP levels between 1 and 3 mg/L and above 3 mg/L are considered coronary disease risk factors (7).

Endothelial dysfunction, known to precede the formation of atherosclerotic plaque, can be assessed in a non-invasive manner in children by peripheral artery tonometry. (8) Only few studies have been performed in obese children with this bed-side technique, showing either normal or a disturbed function, reflected by a lower reactive hyperemia index (9, 10,11) The association with low grade inflammation however was assessed in only one study. We hypothesize that in adolescents and young adults with a history of childhood obesity a more disturbed endothelial function will be present in those with and /or current elevated hSCRP value.

Study Objectives

To investigate whether obese and overweight adolescents with an elevated hs-CRP are more at risk for the development of endothelial dysfunction assessed peripheral artery tonometry, compared to those with a normal hs-CRP at their initial evaluation for obesity-associated metabolic syndrome

To assess the degree of endothelial dysfunction, assessed by the reactive hyperemia index by peripheral artery tonometry in adolescents and young adults with a history of childhood obesity in relation to their current hs CRP value

To investigate the changes in hs-CRP and adiposity in adolescence and young adulthood of initially obese children and adolescents with either normal or elevated hs-CRP levels

Study outcomes

1. Primary outcome

Reactive hyperemia index (RHI) measured by the EndoPAT device

2. Secondary outcome

hs CRP value , BMI z-score and body fat percentage assessed by skinfold thickness

Study design

1. Overall design

This is an observational cohort study

2. Randomization/blinding procedure.

Not applicable.

3. Statistical methodology

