The statistical analysis will be done with the SPSS software.

The difference in THI index between the population with and without low grade inflammation will be evaluated by the Mann Whitney U test and Multivariate analysis of variance, taking current hCRP, age, BMI z-score, and systolic blood pressure into account. The change in hS

CRP in the population with and without low grade inflammation will be analyzed by the Kruskall Wallace test.

The power calculation was done at clincalc.com/stats/samplesize software. Assuming a mean RHI score of 1.51 in overweight children with a standard deviation of 0.2 (9), assuming an equal distribution between the study groups (elevated vs. normal hs-CRP), we have a power of 0.80 to demonstrate a difference of 20 % between the two groups with 27 patients enrolled in each group.

Study population

1. Recruitment

Eligible candidates will be recruited within the children with overweight and obesity having a metabolic risk evaluation before treatment in the period 2006 and 2010 at the pediatric clinic of the UZ Brussel. In total 60 participants will be investigated. Firstly, 30 participating patients with initially elevated hsCRP will be selected at random (following the date of their initial investigation) and afterwards matched for age, BMI z-score, and blood pressure with the same number of patients without initially elevated hCRP values

2. Recruitment procedure

Eligible candidates, or their parents if underage, will be personally contacted by telephone and/or e-mail by their initial pediatric endocrinologist and will be invited to partake in the study. All written information about the study will be provided beforehand.

3. Eligibility criteria

➤ Inclusion Criteria:

- Age 12-21 years at the moment of evaluation
- BMI > 1.3 SDS at the initial evaluation
- Hs-CRP available at initial evaluation

➤ Exclusion Criteria

- Acute or chronic Infection at the time of the study visit

Be or have been a smoker of tobacco

Study intervention

1. Study overview

A single visit is planned. During this visit a standard questionnaire on current health status, life style will be filled in a selfscore of pubertal development using standardized pictures will be done. Standard anthropometrics and blood-pressure measurements , a blooddrawn for hSCRP and a peripheral artery tonometry will be performed.

2. Identification of intervention

➤ Anthropometry:

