The peripheral arterial tonometry can cause a tingling feeling in the occluded arm that will disappear after deflation of the cuff.

Drawing blood may lead to discomfort, pain or a hematoma at the puncture site and syncope.

Quality assurance

EndoPAT device measurements will be done by the same person after training by the technicians. Calibrated instrumented will be used and blood will be drawn according to standard procedures in the University Hospital of Brussel (UZ Brussel). The CRP analysis has a CV of 4.8 % for 1.03 mg/L value.

Privacy policy

The medical file data will be collected after agreement of the responsible treating paediatric endocrinologist. The questionnaire data and medical file data will be merged into an Excel document, which will be protected by a password. All the obtained data will be handled in a confidential way. All names, birth dates and residence data will be erased from the final datafile, which will be stored on a protected server of the UZ Brussel by Prof dr [name], who is the responsible for the data collection and storage. Collected data will be stored for 5 years. The Data Protection Officer of the UZ Brussel ([name] ([contact]) is responsible for further information on data protection. Participants will be informed about the DPO and their right to correct or withdraw collected data.

Publication policy

All publication rights of unprocessed and processed data belong to the investigators.

References

- 2.Wetenschappelijk Instituut Volksgezondheid. Gezondheidsenquête 2013.
- 4.Park MK. Park's pediatric cardiology – sixth edition. Philadelphia: Elsevier Saunders; 2014. 33, Dyslipedemia and other cardiovascular risk factors; p. 520-552.
5. Franks PW et. al. Childhood obesity, other cardiovascular risk factors and premature death. *N Engl J Med.* 2010;362(6):485-93.
6. Visser M et al. Low-grade systemic inflammation in overweight children. *Pediatrics.* 2001 Jan;107(1):E13.

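### Change in hs-CRP is tested between groups defined by one end of that same change, so regression to the mean alone will often give p < 0.05

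*Combined protocol and SAP*

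**What the plan says.** The combined protocol and SAP is the only document. Under Study design, 3. Statistical methodology, the sentence on change in hs-CRP ends: "CRP in the population with and without low grade inflammation will be analyzed by the Kruskall Wallace test". It does not say whether initial or current hs-CRP defines low grade inflammation, or whether change is absolute or on a log scale.

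Study population, 1. Recruitment, forms the groups on the initial value: "30 participating patients with initially elevated hsCRP will be selected at random", and these are then "matched for age, BMI z-score, and blood pressure with the same number of patients without initially elevated hCRP values". hs-CRP is not, and could not be, a matching variable. The synopsis puts the cut at 1 mg/L.

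The test serves the third item under Study Objectives, which concerns "initially obese children and adolescents with either normal or elevated hs-CRP levels", and the secondary objective in the synopsis: "To analyze the changes in hCRP and adiposity in obese children and adolescents after 5 to 10 years". The second item under Study Objectives considers RHI "in relation to their current hs CRP value", so both definitions of the groups are in play in the protocol.

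The covariates in Statistical methodology belong to the RHI analysis, and they include current rather than initial hs-CRP. No repeat initial sample is described.

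**The concern.** A child is placed in the elevated group because one initial measurement was above 1 mg/L. Some of those values will be high for that child, and later values will tend to be lower. The reverse holds in the normal group. The initial value is also subtracted to form the change, so the two groups are expected to change in opposite directions even if nothing has happened in the population. On an absolute scale the normal group also cannot fall by more than 1 mg/L.

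Infection is an exclusion only at the study visit. A transient rise in the initial sample could therefore add to the effect.

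At stake is the reading of a significant result. It would look like inflammation improving in one group and worsening in the other, yet a population with no such pattern often gives the same result. The primary RHI comparison, the sample size, recruitment and data collection do not depend on this test.

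**Working it through.** **The plan's own figure.** There is none for this test beyond the nominal 0.05. The 27 per group in Statistical methodology is for RHI and has no bearing here.

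**Inputs from the protocol.** 30 per group (Recruitment); cut at 1 mg/L and an interval of 5 to 10 years (synopsis); about 20% of overweight children above the cut, as a literature figure (Background); "The CRP analysis has a CV of 4.8 % for 1.03 mg/L value" (Quality assurance).

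**Assumptions.** hs-CRP is log-normal with the same mean and SD at both times, and there is no group effect. The documents do not give the log SD (0.8 to 1.1 tried), the share above the cut in this clinic (20%, 50% and 70% tried) or the initial-to-current correlation r (0.5 to 0.99 tried).

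**Expected change by group.** In units of the log SD, the expected change given an initial value z is −(1 − r)z. With share p above the cut, c the corresponding normal quantile and φ the normal density:

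- elevated group: −(1 − r)φ(c)/p
- normal group: +(1 − r)φ(c)/(1 − p)

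For p = 0.20, c = 0.842 and φ(c) = 0.280. At r = 0.5 the changes are −0.5 × 0.280/0.20 = −0.70 and +0.5 × 0.280/0.80 = +0.175. Simulation gave −0.703 and +0.173.

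**Hand check of the rejection rate (log change, p = 0.20).** The gap between groups is (1 − r) × 0.280/(0.20 × 0.80) = 1.75(1 − r). The SD of change is about √(2(1 − r)). The standardised gap is therefore 1.24√(1 − r), and with 30 per group z = 1.24√(1 − r) × √15.

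- r = 0.5: z = 3.39, rejection about 92%
- r = 0.9: z = 1.52, about 33%
- r = 0.99: z = 0.48, about 8%

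Simulating the Kruskal-Wallis test for the same setting gave 94% and 31% for the first two, and 7–8% at r = 0.99.

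**Full simulation.** 1,500 studies per cell; ranges run over the three shares, log SD 0.8 and 1.1, and absolute or log change. The current grouping reclassifies the same samples.

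| r | Grouped on initial hs-CRP | Grouped on current hs-CRP |
|---|---|---|
| 0.50 | 68–98% | 69–88% |
| 0.70 | 46–86% | 46–67% |
| 0.90 | 20–43% | 23–28% |
| 0.95 | 12–26% | 14–19% |
| 0.99 | 6–12% | 7–11% |

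Grouped on initial hs-CRP, for r up to 0.9, the elevated group shows the relative fall in at least 98.7% of rejections. Grouped on current hs-CRP, the group above the cut shows the larger change in 98–100% of them. A second simulation, with 20,000 studies per cell, 27 or 30 per group and 20% to 50% above the cut, agrees: 78–98% at r = 0.5, 24–43% at 0.9 and 7–12% at 0.99. On the log scale the rate stays near 5% only at r of about 0.998 or more.

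**Assay error alone.** If true values never change and only the 4.8% CV acts, r is about 1 − 0.048²/0.8² = 0.996 at log SD 0.8. The rejection rate is then 5–6% on log change and 8–10% on absolute change. The inflation comes from variation within individuals over years, not from the assay.

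**Check of the alternative.** Current log hs-CRP was regressed on initial log hs-CRP, change in BMI z-score (assumed SD 0.6) and years since evaluation (assumed 8 to 12), the last two unrelated to hs-CRP. Type I error was 4.5–5.5% for BMI z-score change, 4.6–5.5% for years and 4.4–5.8% for a group term if one is added. The mean slope on initial log hs-CRP recovered r (0.50, 0.70, 0.90). Selecting patients on initial hs-CRP is selection on the predictor, so it does not bias this slope.

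**The case against.** The strongest objection is to calling these rates false positives. If individuals truly move over the years, expected change does differ between the groups, so rejecting equal change is correct and only the interpretation is wrong. That is a fair point about wording. The rates are best read as how often a stationary population with no group effect gives p < 0.05. The practical problem is the same, since the test cannot separate that population from one with a real group difference in change.

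The only within-person error that the protocol quantifies is the assay CV, and it causes almost no inflation on the log scale. The large figures rest on assumed values of r. Both statements stand. Even so, the inflation is small only if tracking is almost perfect over 5 to 10 years.

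Part of the absolute-scale excess is not regression to the mean. With r close to 1 the rate is still about 7–8%, because change is more variable in the elevated group. This stands, but it matters little at r of 0.9 or below.

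The simulations ignore the matching. The sentence could also be read as a within-group or multi-category analysis. Neither point removes the shared hs-CRP value.

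The objective is exploratory, and no claim of improvement by group is planned. That limits the severity. It does not make the one named test for this objective interpretable. Finally, the extra predictors proposed below are not needed to remove the artefact; conditioning on initial log hs-CRP is.

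**Conclusion.** The concern holds, and the analysis is wrong as written. Under stationary log-normal hs-CRP with 30 per group and groups formed on the initial value, the planned test gives p < 0.05 in 68–98% of studies at r = 0.5, 20–43% at r = 0.9 and 6–12% at r = 0.99. Using current hs-CRP to define the groups does not help. The size depends on r, which the documents do not give; the direction does not. This should be fixed, but it is confined to the hs-CRP part of a secondary objective.

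**What to change.** In Statistical methodology, state that low grade inflammation here means initial hs-CRP above 1 mg/L, if that is intended. Remove the between-group test of raw change and replace it with:

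1. A regression of current log hs-CRP on continuous initial log hs-CRP, with change in BMI z-score and years since the initial evaluation as further predictors.
2. The proportions still above and newly above 1 mg/L, and the within-group changes, with confidence intervals, labelled as descriptions of tracking only.

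The second part carries the same artefact, and the text should say so. With 20% above the cut, a stationary population gives about 44% still above and 14% newly above at r = 0.5 (0.20 × 44% + 0.80 × 14% = 20%, as it must be). At r = 0.9 the figures are about 75% and 6%. The report should not claim that inflammation improved or worsened by group.

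No new data are needed. Initial hs-CRP is an inclusion requirement, current hs-CRP is measured at the visit, BMI z-score is available at both times, and the initial dates are already used for selection. The amendment falls under Ethical and regulatory information, 9. Protocol amendments: "Changes to the study protocol will be submitted to the Ethics Committee and will not be performed before obtaining an approval". The cost is that the raw change comparison is no longer tested.

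### The only analysis named for change compares hs-CRP change between groups formed on initial hs-CRP: it cannot show whether, which way or how far hs-CRP moved, and nothing is named for adiposity

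*Combined protocol and SAP*

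**What the plan says.** The synopsis gives one secondary objective: "To analyze the changes in hCRP and adiposity in obese children and adolescents after 5 to 10 years". The Study Objectives section words it by initial group: "To investigate the changes in hs-CRP and adiposity in adolescence and young adulthood of initially obese children and adolescents with either normal or elevated hs-CRP". Study outcomes lists the secondary outcomes as "hs CRP value , BMI z-score and body fat percentage assessed by skinfold thickness".

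Study design, 3. Statistical methodology, names one analysis of change. The change in hs-"CRP in the population with and without low grade inflammation will be analyzed by the Kruskall Wallace test". The other methods in that section, the Mann-Whitney U test and a multivariate analysis of variance, are for the reactive hyperemia index (typed there as THI). No within-patient test, no estimate of change with an interval, and no analysis of change in adiposity is named.

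Study population, 1. Recruitment, fixes the groups. Thirty patients with initially elevated hs-CRP are chosen, "afterwards matched for age, BMI z-score, and blood pressure with the same number of patients without initially elevated hCRP values". The synopsis puts the cut-off at 1 mg/L. The eligibility criteria require an initial BMI and an initial hs-CRP, but not initial skinfolds.

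**The concern.** The objective asks what happened to the same people over time. The Kruskal-Wallis test compares independent groups. The sentence allows two readings, and neither meets the objective.

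- **Change scores compared between groups.** The test asks only whether the two distributions of change differ. An equal rise in both groups gives a null result. A significant result implies that at least one group moved, but not which group, in which direction or by how much.
- **Initial and current values compared within a group.** Two values from one patient are treated as independent, and the pairing is lost.

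On the first reading there is a further problem. The initial hs-CRP both defines the group and enters the change score. Patients chosen for a high value will on average be lower later, and those chosen for a low value higher, even if the population has not changed. The test is then likely to be significant for that reason, and the result could be reported as a different natural course of inflammation.

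For adiposity, the other half of the objective, the analysis would have to be chosen after the data are seen.

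**Working it through.** The plan gives no sample size or power for this objective, so there is no figure of its own to reproduce. The checks use the planned 30 + 30 patients.

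**1. Is the test blind to a shared change?** Change scores were drawn as normal with SD 1 and the same mean shift in both groups, with 3,000 trials per row.

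| Common change (SD of change) | Kruskal-Wallis rejects | Signed-rank within one group rejects |
|---|---|---|
| 0 | 5.1% | 5.3% |
| 0.5 | 4.8% | 73% |
| 0.8 | 4.6% | 98% |
| 1.0 | 4.4% | over 99% |

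The between-group test stays at its nominal level throughout. With two groups it is the Mann-Whitney test under another name: on one check data set both gave p = 0.344.

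**2. What does regression to the mean do?** Assumptions, none of them given in the documents:

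- Log hs-CRP is normal at both times with equal mean and SD, so there is no true population change.
- The initial-to-current correlation ρ is 0.3 to 0.7.
- The share p of the clinic population above the cut-off is 20% to 70%. The background says low grade inflammation "was found to be present in 20.6 % and 19.8 % of overweight children and adolescents", but states no cut-off for that figure and gives no share for this clinic, so a range is needed.
- Patients within each group are drawn at random.

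With c = Φ⁻¹(1 − p), the mean initial value in SD units is φ(c)/p in the elevated group and −φ(c)/(1 − p) in the normal group. The expected change in each group is −(1 − ρ) times that mean.

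For p = 0.20, φ(c) = 0.280, so the means are 0.280/0.20 = 1.40 and −0.280/0.80 = −0.35. At ρ = 0.5 the elevated group changes by −0.5 × 1.40 = −0.70 SD and the normal group by +0.5 × 0.35 = +0.175 SD. The difference is −0.875 SD with nothing having happened.

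The table gives the expected spurious difference (elevated minus normal, in SD of log hs-CRP) and the Kruskal-Wallis rejection rate in 4,000 simulated trials per setting.

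| Share elevated | ρ = 0.3 | ρ = 0.5 | ρ = 0.7 |
|---|---|---|---|
| 20% | −1.225; 99% | −0.875; 94% | −0.525; 75% |
| 35% | −1.140; 98% | −0.814; 91% | −0.488; 68% |
| 50% | −1.117; 98% | −0.798; 89% | −0.479; 67% |
| 70% | −1.159; 98% | −0.828; 92% | −0.497; 71% |

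**3. Does matching alter this?** Normal patients were instead matched on BMI. BMI was assumed to correlate 0.3 or 0.5 with initial and 0.1 or 0.4 with current log hs-CRP, with p of 20%, 50% or 70% and 2,000 trials per setting. At ρ of 0.3 and 0.5 the rejection rate was 64% to over 99%. At ρ = 0.7 it was 53% to 86%, except for the pairing 0.5 and 0.1, where it fell to about 14% to 15%. The artefact is usually large, but its size depends on correlations that the documents do not give.

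**4. The other reading, ignoring the pairing.** For a true shift of 0.5 SD in 30 patients, a paired t-test has noncentrality 0.5√30/√(2(1 − ρ)), which gives power of 61%, 75% and 93% at ρ = 0.3, 0.5 and 0.7. The unpaired formula, with noncentrality 0.5√15, gives 48%.

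**5. Adiposity.** The objective in both places and the list of outcomes set against the statistics section show two outcomes, BMI z-score and body fat, with no analysis of change.

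**The case against.** The Study Objectives wording refers to children with either normal or elevated hs-CRP, so a comparison between those groups addresses part of the objective. That stands: for hs-CRP the plan is not silent. But the same wording is met more directly by reporting change within each group, which the plan does not do.

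A reader might infer that the equal split of the sample, set against the background figure of about 20%, means that the trial will report a false fall in hs-CRP. The documents do not support this. No section plans a change pooled over both groups. If one were computed with no true change, the 50:50 mean would be −0.37 to −0.16 SD at a 20% share, zero at 50%, and +0.23 to +0.10 SD at 70% (ρ from 0.3 to 0.7). Even the sign depends on a share that is not given.

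A reader might also infer that weighting the two groups by the clinic's share gives an unbiased cohort estimate. It would if the normal group were a random sample, but that group is matched on age, BMI z-score and blood pressure. With matching on BMI alone, a 20% share, ρ of 0.3 to 0.5 and no true change, the weighted estimate ran from about −0.22 to +0.08 SD.

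Finally, this is a secondary objective without a power claim, and the primary comparison of the reactive hyperemia index is untouched. That limits the weight of the point but does not remove it.

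**Conclusion.** The point holds in this form. The one analysis named for change cannot say whether, in which direction or by how much hs-CRP changed. That conclusion follows from the nature of the test and needs no assumption. The lack of any analysis for change in BMI z-score and body fat is likewise plain from the text.

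The size of the regression-to-the-mean problem is conditional. Under the normal model with randomly drawn groups, the between-group test is significant in about 67% to 99% of trials without any true population change. Matching on BMI widens that range, with low rates in one combination of assumed correlations. I read the groups as defined by initial hs-CRP because recruitment forms them that way; the statistics sentence does not say so itself.

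It does not follow that the trial will report a spurious overall fall, or that the primary result is affected. The plan should be changed because a better analysis is available from data already to be collected.

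**What to change.** Replace the Kruskal-Wallis sentence in Study design, 3. Statistical methodology, with:

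> For each participant we will compute log(current/initial hs-CRP) and the change in BMI z-score, and the change in body fat percentage where initial skinfolds are on file, stating the number available. The paired mean change with 95% confidence interval (or the Wilcoxon signed-rank test) will be reported within each initial hs-CRP group. Because the groups are defined by initial hs-CRP, within-group and between-group changes in hs-CRP are descriptive and will be reported with a statement that regression to the mean is expected. A between-group test of hs-CRP change will not be read as evidence of a different evolution.

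Add that an unweighted change pooled over the 50:50 sample will not be presented as the change in the clinic population. A version weighted by the clinic's own share of elevated initial values may be added as a sensitivity analysis only, with the limit set by matching stated.

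The cost is slightly more analysis work and a more modest conclusion on hs-CRP change. No extra patient, visit or measurement is needed. The optional weighted version also needs a count of elevated and normal initial values in the 2006 to 2010 files.

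### The power statement contradicts its own inputs: at mean 1.51 and SD 0.2, a 20% difference needs 7 to 8 per group, and 27 per group gives 80% power for about 10%

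*Combined protocol and SAP*

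**What the plan says.** Study design, 3. Statistical methodology, gives every input but one. The starting point is "Assuming a mean RHI score of 1.51 in overweight children", with an SD of 0.2 taken from the plan's reference 9 and equal-sized groups with elevated and normal hs-CRP. The conclusion is that "we have a power of 0.80 to demonstrate a difference of 20 % between the two groups with 27 patients enrolled in each group".

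The Sample Size row of the synopsis supplies the missing input, alpha, and the matching total: "54 (α= 0,05 – power 80" per cent. Sidedness is not stated.

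The same methodology section names the Mann-Whitney U test, with a multivariate analysis of variance, for the comparison of the two groups. Study population, 1. Recruitment, plans 60 participants, 30 with initially elevated hs-CRP and 30 matched without. No dropout rate is given, and nothing links the 60 to the 54.

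**The concern.** Against an SD of 0.2, a 20% difference on a mean of 1.51 is a very large standardised effect (1.51 SD). Such an effect needs only a handful of patients per group, so 27 per group at 80% power looks wrong on sight.

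The possible corrections describe different studies:

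- **If SD 0.2 is right**, the study can detect about half the difference it claims. A null result would then be much more informative than the protocol suggests.
- **If 20% was the intended target**, the SD used must have been about twice the printed one. A reader relying on 0.2 would expect twice the precision the study can deliver. Power for a 10% difference at 27 per group would be only about 0.28.

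The paragraph is the only sample-size justification for the primary outcome, and the synopsis repeats its result.

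**Working it through.** **Inputs.** Mean 1.51, SD 0.2, difference 20%, power 0.80, 1:1 groups and 27 per group come from Statistical methodology. Alpha 0.05 and the total of 54 come from the synopsis. Two-sided alpha is our assumption; one-sided is tried below.

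**Step 1. Try to reproduce 27 per group.**
Difference = 0.20 × 1.51 = 0.302; standardised, 0.302 / 0.2 = 1.51.
n per group = 2 × ((1.960 + 0.842) × SD / difference)²
= 2 × (2.802 × 0.2 / 0.302)² = 6.88, so 7.
The exact t-test gives 7.97, so 8. The plan's 27 is not reproduced.

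**Step 2. Power at 27 per group for 20%.**
Standard error = 0.2 × √(2/27) = 0.0544; 0.302 / 0.0544 = 5.55; 5.55 − 1.96 = 3.59, which gives power of 0.9998. The t-test also gives 0.9998, and a simulated Mann-Whitney test under normality gives 0.9997.

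**Step 3. Difference detectable with 27 per group at 80% power, SD 0.2.**

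| Method | Difference | % of 1.51 |
|---|---|---|
| Normal: 2.802 × 0.2 × √(2/27) | 0.152 | 10.1 |
| t-test | 0.155 | 10.3 |
| Mann-Whitney, efficiency 0.955 | 0.159 | 10.5 |

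**Step 4. Which inputs come close to 27?**
- 10% difference (0.151), SD 0.2: n = 2 × (2.802 × 0.2 / 0.151)² = 27.54 (t-test 28.5). Power at 27 is 0.79 (normal), 0.78 (t-test) and about 0.76 (Mann-Whitney).
- 20% difference (0.302), SD 0.4: the standardised effect is the same (0.755), so n and power are the same.
- SD at which 20% needs exactly 27: 0.302 / (2.802 × √(2/27)) = 0.396 (normal) or 0.389 (t-test).

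**Step 5. Other readings of the 20%, SD 0.2, 80% power.**

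| Reading | n per group |
|---|---|
| One-sided alpha, 20% | 5.4 by the normal formula, so 6; t-test 7 |
| Absolute difference of 0.20 RHI units | 16 to 17 (power at 27 about 0.95) |
| 1.51 as the higher mean, the other 1.51/1.2 | 10 to 11 |
| 1.51 as the lower mean, the other 1.51/0.8 | 5 to 6 |
| Mann-Whitney, two-sided, 20% | 9 (10 at worst-case efficiency 0.864) |

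None reaches 27.

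**Step 6. At the planned 30 per group.** For a 10% difference at SD 0.2, power is 0.82 by t-test and about 0.80 by Mann-Whitney. The difference detectable by t-test is 0.147 (9.7%).

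**The case against.** The arithmetic is not in dispute, but four points can be made for the plan.

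- **Diagnosis.** The documents show only that difference, SD, power and n conflict. They do not show which is wrong; n could be the faulty figure, or more than one input. This stands. A factor of two in the difference or the SD is the closest fit, but not an exact one, since 27.54 rounds up to 28.
- **Adequacy.** In either scenario the study keeps roughly 80% power for a 20% difference: above 99.9% at SD 0.2, and at SD 0.4 by t-test 0.78 with 27 per group or 0.82 with 30. Underpowering for the stated target is therefore not shown. This also stands, but the fault is that the stated power is not the power the printed inputs give.
- **Consequences.** The final confidence interval will come from the observed SD, and a single-visit observational study places little burden on surplus participants. True, but the plan still gives no reliable statement of the difference it was sized to find.
- **Remedy.** Restating the target as 10.5% fits the effect to an existing n, and an SD of about 0.4 is inferred, as neither the calculator inputs nor the cited study are available here. Treating 54 as evaluable out of 60 recruited is also an inference. These points are fair, and they are why the correction has to be conditional on what the sponsor confirms.

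**Conclusion.** The concern holds. On the plan's own mean, SD and alpha, 20% at 80% power needs 7 to 8 per group (about 9 with the planned Mann-Whitney test). The stated 27 is more than three times the t-test figure (27 / 8 = 3.4). At 27 per group the power for 20% is 0.9998, and 80% power corresponds to a difference of about 10% (0.152 to 0.159 RHI units).

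This rests on two-sided alpha 0.05, equal groups and a common SD. One-sided testing widens the gap, and the Mann-Whitney allowance does not close it. The most economical explanation is a factor of two in the printed difference or the printed SD; the documents do not settle which. The statement must be corrected, because it is the sole basis for the sample size and it reports a power that its inputs do not give.

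**What to change.** Check what was entered in the online calculator, then correct the sentence in Statistical methodology and bring the synopsis into line:

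- **If SD 0.2 is confirmed:** state that 27 per group gives 80% power for a difference of about 0.16 RHI units (10.5% of 1.51) at two-sided alpha 0.05 with the Mann-Whitney test. Present this as the detectable difference; nothing in the documents establishes it as the difference of interest.
- **If 20% was the intended difference:** replace 0.2 with the SD actually entered (about 0.4 by back-calculation) and give its source. At SD 0.4 the Mann-Whitney test has power of about 0.76 with 27 per group and about 0.80 with 30.
- **In either case:** state sidedness and the test assumed, and say once how 54 relates to 60. If the intention is 54 evaluable out of 60 recruited, say so.

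The cost is one sentence and one synopsis entry, with no extra patients. The exception is if the SD proves to be near 0.4 and the sponsor wants to detect 10%: the present size would not do that.
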